9. STUDY TIMELINES*

The duration of an individual subject's participation in the study is 6 months (baseline survey, texting system, quitline data, and the 6-month follow-up survey). For those asked to complete the qualitative interview, this will take no longer than one hour after they have completed the six-month follow-up survey. The duration anticipated to enroll all study subjects is 2 years, 2 months. The estimated date for the investigators to complete this study with primary analyses is: the middle of year 5 (55 months).

10. STUDY ENDPOINTS*

The main dependent variable is patient tobacco cessation rate (quit rate) at six months. The primary independent variable is assignment to intervention or comparison group. We have designed a patient-level analysis around point prevalence cessation. We will use a two-sided chi-square test for equality of proportions to test whether the quit rates differ between the groups. If we need to adjust for any covariates, we will include them in a multivariable logistic regression model with smoking cessation as the outcome and group status as the main independent variable. Our secondary outcome measure is self-efficacy. We hypothesize that the self-efficacy (SEQ-12) scores will be higher in intervention than comparison. The SEQ-12 is a 12-item questionnaire with 6 questions under two domains, internal and external stimuli. Two composite scores are

INVESTIGATOR STUDY PLAN - REQUIRED

computed for each of these domains by adding the individual items. These data will be collected at baseline and at the follow-up. The aim is to assess the effect of intervention over the immediate period, i.e., do the scores improve more from baseline to six months for the intervention group than the control group. We will compute the scores at baseline six months in the two groups.

11. PROCEDURES INVOLVED*

Patient recruitment will be conducted by clinical services staff (staff in clinic and their affiliated community health workers). At the beginning of the study, all study personnel and community and quitline collaborators will be trained carefully about study protocol and standard operational procedures (SOP). Treatment fidelity will be determined by the Vietnam Co-PIs directly monitoring 20% of all study enrollment and follow-up visits and completing a fidelity checklist. As noted, as 27% of Vietnamese male and female smokers have not been to a clinic in the past year, we will recruit both through clinic staff and through outreach community health workers. Sampling frames (household/resident lists) that comprise all adult community members will be obtained from commune records. Based on the sampling frame, adult commune residents will be randomly selected for screening for smoking status. To minimize selection bias, enrollment of patients will proceed in a systematic and sequential manner until the full sample size has been attained. Patients who agree to participate will complete informed consent procedures, baseline survey, and will be provided a text-enabled phone as needed.

Randomization: Participants will be blinded to randomization. All smokers will be told that they will be randomized to one of two different ways to support thinking about quitting smoking. In addition to our primary points of innovation, we will use an innovative mHealth randomization strategy. Allocation of participants to study arms will be based on a permuted block scheme in which treatment assignments are made within blocks so that numbers assigned to each treatment arm are equal after a block has been filled. Blocks of various sizes (2, 4, 6) will be used in random order to facilitate allocation concealment. Similar to our prior technology-based trials, we will embed randomization within the technology. At enrollment, study staff will conduct a baseline survey with participants. At the end of the baseline assessment survey, study staff will enter the participant ID and participant mobile phone number from the survey into our texting system, and the system will look up the next allocation within the table, and adapt based on the allocation assignment. Using this technique, both smokers and the study staff will be blinded to allocation during the initial session. In our prior technology-assisted randomized trials, we have embedded randomization within the technology.

INVESTIGATOR STUDY PLAN - REQUIRED

Baseline data collection (see M2Q2_Baseline_Survey): will include patient demographics, comorbidities, cessation treatment beliefs scale, and self-efficacy. Self-efficacy will be measured with the SEQ-12.^[36] The SEQ-12 is a 12-item questionnaire with 6 questions pertaining to internal stimuli and external stimuli domains each. Two composite scores are computed for each of these domains by adding the individual items. Self-efficacy will be assessed at baseline and follow-up.

Measures through texting: as described above, we will have data collected through texting, including measure of readiness to quit, abstinence assessments, and interest in use of the quitline.

Quitline referral tracking – quitline staff will record details of intake assessment (time on call, readiness to quit, quit date and goal-setting) and fidelity of follow-up call completion. They will also document distribution of NRT lozenge and smoker use of NRT during follow-up.

Follow-up: All participants will be followed-up with 6 months post-enrollment. To minimize losses to follow up and missing data, one week before the scheduled follow-up visit study staff will contact participants by either phone to remind them about their subsequent clinic visits. For participants who miss the follow up visits at the clinic, trained study staff will conduct the interview via telephone. Biochemical verification of smoking cessation will not be obtained for participants completing the follow-up interview via telephone.

6-month data collection (see M2Q2_6moSurvey): A paper survey will be used to collect repeat data on key baseline measures (SEQ-12), and measure smoker perceptions of the intervention supporting smoking cessation. Study staff will determine current smoking through self-report (7 day point prevalence cessation) based on the following question “Do you currently smoke cigarettes (smoked even 1 puff in the last 7 days)?” and then verify with a carbon monoxide breath monitor.^[37] Patients who respond “no” to smoking now will be classified as non-smokers if their carbon monoxide measurement is less than 10ppm. For participants conducting the interview via phone, staff will collect and enter data via REDCap.

Qualitative Interview (see document titled “M2Q2_QI_Guide”): We will conduct a detailed qualitative interview with up to 30 participants to identify potential facilitators and barriers to study participation. Interviews will be conducted in-person at community health centers of participating study sites or by phone. We will audio-record interviews; the audio-recorded interviews will be transcribed and entered into NVivo 10 qualitative analysis software. We anticipate that each interview will take up to one hour. We will review these results as a group to make appropriate protocol changes. Participants will

INVESTIGATOR STUDY PLAN - REQUIRED

be provided an incentive of \$15 to participate in the semi-structured individual interviews. All United States Dollar amounts are approximate due to the conversion rate to Vietnamese dong.

12. DATA AND SPECIMEN BANKING*

N/A

13. DATA ANALYSIS AND MANAGEMENT*

Power calculations are based on having complete data on a sample of 600 for the intent-to-treat analysis. Note that for our analysis with missing = smoking, we will use the full sample randomized. As discussed above, all participants randomized to the intervention will receive the motivational messages. However, participants will choose whether or not to use the quitline and NRT.

Our calculations are based on several assumptions. First, in the U.S., rates of cessation without intervention have been documented to be 7-10% per year.^[38] In Vietnam the rate of smoking is high, and the annual rate of cessation is low. To be conservative, we have estimated the control cessation rate to be 10%. Based on our prior trials, we have detected a 9% difference in intervention and control, comparing the motivational messaging system with a robust, website-only control (as we have a simple attention control in this study, the difference may be greater). If we anticipate that 30% of the intervention will engage in quitline counseling and NRT, and that group will have a greater cessation rate (between 20 to 25%), then the overall cessation rate averaged across the intervention group will be greater than 10%. Based on these assumption, we have assessed power for a range of assumptions (with difference in cessation from 7% to 10%). We are powered to detect a 10% difference (alpha at 0.05) with 91% power.

To preserve the power of randomization, all primary analyses will be on an intent-to-treat basis. However, secondary analyses will explore dose-response effects among those with variable levels of adherence to the intervention. All analyses will be two-sided and alpha error will be set at 0.05. We will begin the statistical analysis by examining univariate statistics (means, medians, standard deviations and 95% confidence intervals) and distributions. We will examine the balance of participant characteristics by study groups and account for any imbalances in our multivariable analysis. As appropriate, group differences will be tested using chi-square tests of independence (categorical variables), Z-test or t-test (continuous variables) or the equivalent non-parametric tests depending on the distribution of the variables. In accordance with best practice, differences in baseline characteristics of the intervention and comparison groups will be established based on standardized differences, rather than on tests of statistical significance.^[39, 40]

Main outcome: six-month point prevalence cessation: The main dependent variable is patient tobacco cessation rate (quit rate). The primary independent variable is assignment to intervention or control group. We have designed a patient-level

INVESTIGATOR STUDY PLAN - REQUIRED

analysis around point prevalence cessation. We will use a two-sided chi-square test for equality of proportions to test whether the quit rates differ between the groups. If we need to adjust for any covariates, we will include them in a multivariable logistic regression model with smoking cessation as the outcome and group status as the main independent variable.

Because we are interested in the effect of the intervention in the sample targeted, we will conduct an intent-to-treat analysis with all those randomized analyzed from MHV use at follow-up. As many in the encouragement arm will not participate, this ITT does not directly assess the intervention-attributable effect. Thus, in addition to ITT, we will utilize a complier average causal effect (CACE) analysis to estimate intervention effects for those who engaged with the intervention.^[41] CACE estimation makes it possible to estimate the intervention effect for only those who engage. The CACE estimation considers both random assignment and receipt of treatment to estimate intervention efficacy. CACE estimations have been published using instrumental variables, expectation-maximization algorithm, maximum-likelihood, and integrated methods.^[42] CACE seeks to compare outcomes for individuals in the intervention condition with those who would have complied with treatment given the opportunity to do so, and can often be used to improve power over ITT methods. Below, we provide power for ITT analyses, and anticipate additional power when implementing the CACE.

Dealing with missing outcomes data: We will make every effort to maximize participant retention in the study. For our short-term evaluation, we do not expect high rates of attrition; however, we approximate that there will be about 15-20% attrition based on previous studies. Thus, although we plan to randomize 750, our power calculations for outcomes are based on 600 completing follow-up. We will monitor recruitment and retention, and inflate our sample as needed to achieve the resulting sample of 600 completing 6-months. We will estimate potential bias due to drop-outs in our study and perform a series of sensitivity analyses to understand the extent of this bias. We will assess the extent of missing data by treatment group for each time point. A challenge for all cessation induction trials is missing outcome data.^[43-45] This is especially true in light-touch technology-assisted interventions. Most often, a complete case or missing case (penalized imputation) indicative of smoking analysis has been implemented in logistic regression. However, the reason that we did not use penalized imputation as the primary outcome is that new literature has been published suggesting that penalized imputation (or missing=smoking) is not a conservative approach, and can be biased toward the intervention.^[44] Thus, for studies with missing cessation data greater than 10-20%, experts recommend using selection models to examine the robustness of findings.^[43] We will compare characteristics of patients who remained in the trial and those lost to follow-up. Using a generalized linear model with a logit link to evaluate cessation outcomes and GEE methods to account for clustering within practices, we will

INVESTIGATOR STUDY PLAN - REQUIRED

implement a selection model using inverse probability weighting to determine the potential effect of missing data. First, based on covariates available within the dataset, we will develop a logistic regression model to predict the amount of missing data. Then, we'll calculate the inverse probability of not being missing and weight the main analysis by this probability.^[46]

Secondary Outcome: Self-efficacy: We hypothesize that the self-efficacy (SEQ-12) scores will be higher in intervention than comparison. The SEQ-12 is a 12-item questionnaire with 6 questions under two domains, internal and external stimuli. Two composite scores are computed for each of these domains by adding the individual items. These data will be collected at baseline and at the follow-up. The aim is to assess the effect of intervention over the immediate period, i.e., do the scores improve from baseline to six months for the intervention group than the control group. We will compute the scores at baseline six months in the two groups. We will evaluate whether the intervention differences change over time (i.e., is there an intervention and time interaction?). To address this question, we will use a random-effects model of the form:

$$y_{ijt} = \alpha + \gamma_i + \beta_j + \delta_t + (\beta\delta)_{it} + u_{ij} + e_{ijt}$$

where, y_{ijt} is response at time t for the j -th subject in the i -th group, α is the intercept, γ_i is the vector of effects associated with covariates, β_j is the main effect for the intervention group, δ_t is the main effect for time, $(\beta\delta)_{it}$ is the effect for the interaction between intervention group and time, u_{ij} is the random effect corresponding to the j -th subject in the i -th group (assumed to be $N(0, \sigma_u^2)$), and e_{ijt} is the term accounting for sampling variability (assumed to be $N(0, \sigma_e^2)$). The coefficient $(\beta\delta)_{it}$ is the estimate of the interaction term which, if significant, indicates that the intervention effect varies significantly with time. We will first generate the variance-covariance matrix to determine the appropriate covariance structure.

Portable devices used to collect data (audio recordings from qualitative interviews) will be PHAD-issued devices and files will not be encrypted during the recording, but the recordings will be transferred as soon as possible (i.e.: typically within the same day) to REDCap. Once the files are transferred, they will be deleted from the portable devices. Data gathered through qualitative interviews will be managed and coded using NVivo 10. An integrated approach to coding will be used, employing a coding start-list based on protocol questions (deductive coding) and open coding driven by emersion in the qualitative data (inductive coding). Duplicate coding will be conducted with at least 10% of the interview transcripts and coding comparisons will be run to ensure inter-rater reliability. Disputes in coding decisions will be discussed within the research group until resolved. We will continue to test and refine coding until we attain a Kappa $>.80$. NVivo qualitative analysis software will be employed to generate coding reports that summarize participant responses, ideas, and reflections related to

INVESTIGATOR STUDY PLAN - REQUIRED

relevant research questions. Two members of the research team will complete the thematic analysis.

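### Covariates for the six-month quit-rate analysis are to be chosen from observed imbalance, with no cut-off, covariate list or named primary result; a fixed adjusted model costs nothing and gains a little power

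*Combined protocol and SAP*

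**What the plan says.** Section 10 (Study Endpoints) and Section 13 (Data Analysis and Management, main outcome) both name a two-sided chi-square test of equal proportions for the six-month quit rate. Both then add: "If we need to adjust for any covariates, we will include them in a multivariable logistic regression model". Section 13 also states how covariates are to be found: "We will examine the balance of participant characteristics by study groups and account for any imbalances in our multivariable analysis". Imbalance is to be judged by standardised differences and not by significance tests. No threshold is given.

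The general rule on error is "All analyses will be two-sided and alpha error will be set at 0.05". Neither section says which covariates are candidates, what would create a need to adjust, or which result decides the trial if the chi-square and the logistic model disagree.

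The paragraph on missing outcomes in Section 13 mentions a further model, a logit-link GEE with clustering by practice, and applies inverse-probability weights to what it calls the main analysis. It does not say which of the analyses above that is.

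Section 11 lists the baseline survey content as demographics, comorbidities, treatment beliefs and self-efficacy (SEQ-12). The survey is finished before the texting system allocates the participant. Randomisation uses permuted blocks, with no stratification factor named.

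**The concern.** In a randomised trial, a difference between arms at baseline is due to chance. What makes a covariate worth adjusting for is how strongly it predicts quitting, not whether it happens to differ between arms. A strong predictor that is well balanced still improves precision; an imbalanced variable unrelated to quitting adds nothing. A trigger based on imbalance therefore picks covariates on the wrong property, and does so after the arms have been compared.

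Two things are at stake. The first is discretion: with no cut-off, list or ranking, the analysis team can decide late which p-value counts. The reported effect may also change from a comparison of proportions to a covariate-conditional odds ratio. The second is precision: baseline predictors are collected before allocation, but none is committed to the quit-rate analysis.

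**Working it through.** **Inputs from Section 13.** "Power calculations are based on having complete data on a sample of 600 for the intent-to-treat analysis", so 300 per arm under 1:1 allocation. Control rate: "we have estimated the control cessation rate to be 10" per cent. Range considered: "with difference in cessation from 7% to 10" per cent. Two-sided alpha 0.05.

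**Stated power.** The plan says "We are powered to detect a 10% difference (alpha at 0.05) with 91% power". For 10% v 20%, the mean rate is 0.15.
- Null standard error: √(2 × 0.15 × 0.85 / 300) = 0.02915; times 1.96 = 0.05714.
- Alternative standard error: √((0.09 + 0.16) / 300) = 0.02887.
- With continuity correction: (0.10 − 1/300 − 0.05714) / 0.02887 = 1.369, power 91.5%. This reproduces the 91%.
- Without correction: 1.485, power 93.1%.
- The same uncorrected formula for 10% v 17% gives 70.9%.

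The stated power is thus that of an unadjusted two-proportion comparison.

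**Chance that the trigger fires.** A standardised difference has standard error √(2/300) = 0.0816. The cut-offs are assumed, because the plan gives none.
- Cut-off 0.1: p = 2 × (1 − Φ(0.1/0.0816)) = 0.2207 per covariate.
- Cut-off 0.2: p = 0.0143 per covariate.
- At least one of k independent covariates: 1 − (1 − p)^k.

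| Covariates | 0.1, 300 per arm | 0.2, 300 per arm | 0.1, 375 per arm | 0.2, 375 per arm |
|---|---|---|---|---|
| 4 | 63% | 6% | 53% | 2% |
| 8 | 86% | 11% | 78% | 5% |
| 12 | 95% | 16% | 89% | 7% |

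The 375 columns apply if balance is judged on all 750 randomised (p = 0.1709 and 0.0062). The unstated cut-off alone moves an adjusted analysis from unlikely to almost certain.

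**Type I error.** Simulation: 600 participants, 10 baseline covariates of which 3 are prognostic, 15,000 null trials per setting. Prognostic strength is assumed, from log-odds per SD of 0.4/0.3/0.3 (weak) to 0.8/0.6/0.5 (strong). At cut-off 0.1:
- Chi-square: 5.3% (weak), 4.9% (strong).
- Imbalance rule applied mechanically: 5.0% (weak), 4.4% (strong).
- The two verdicts differ in 1.5% (weak) and 2.1% (strong) of null trials.
- Rejection by either test = (chi-square + triggered + differing) / 2. Weak: (5.33 + 4.95 + 1.54)/2 = 5.9%. Strong: (4.90 + 4.35 + 2.11)/2 = 5.7%.
- At cut-off 0.2 the same sum gives 5.4% and 4.9%, because the trigger rarely fires.

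**Power.** Same simulation, 8,000 trials per setting, cut-off 0.1:

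| Rates | Strength | Chi-square | Imbalance rule | Pre-specified model |
|---|---|---|---|---|
| 17% v 10% | weak | 71.5% | 70.9% | 72.5% |
| 17% v 10% | strong | 71.7% | 72.6% | 77.3% |
| 20% v 10% | weak | 93.1% | 93.5% | 94.1% |
| 20% v 10% | strong | 93.7% | 94.3% | 96.3% |

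The pre-specified model gains about 1 point over the chi-square with weak predictors. With strong ones it gains about 5 points at the 7-point difference and 2 to 3 points at the 10-point difference. The imbalance rule stays close to the chi-square throughout. At 17% v 10% with cut-off 0.1, the chi-square and the triggered model reach different verdicts in 5.1% (weak) to 7.6% (strong) of trials.

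**Can the data carry a fixed model?** Expected quitters: 300 × 0.10 + 300 × 0.17 = 81, or 30 + 60 = 90 at the larger difference. Arm, sex, linear age, four communes (3 terms) and two SEQ-12 scores make 8 coefficients, about 10 to 11 quitters for each.

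**The case against.** The best defence is that the chi-square is named first and without condition, and that the stated power matches a two-proportion test. On that reading it is the primary analysis and the logistic model is a supplement. Nothing says that the model would replace it. This is a fair reading, but the text does not state it, and the sentence on imbalances is a commitment to adjust. Preferring standardised differences to significance tests is sound, but it settles only how imbalance is measured.

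The defence is right that the harm is limited. A reader might infer four stronger points that the documents do not support:
- That the adjusted model would usually displace the chi-square. This holds only at a cut-off near 0.1, which the plan never states; at 0.2 it would be uncommon.
- That the rule inflates type I error. Applied mechanically it does not. The excess needs selective reporting of the better test, which the plan does not propose.
- That the estimand moves between a marginal and a conditional odds ratio. The chi-square compares proportions, and the plan names no marginal odds ratio.
- That readiness to quit is measured only after randomisation. Section 11 lists it through texting ("including measure of readiness to quit, abstinence assessments, and interest in use of the quitline") and at quitline intake, and it is absent from the summary of baseline content. But the baseline survey form is not among the documents and may ask it. The plan nowhere proposes to adjust for readiness reported by text.

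It also stands that the documents do not say how strongly sex, age, commune or SEQ-12 predict quitting here, so the power gain is a range under assumption. Declaring the chi-square primary would by itself remove the discretion; it would leave the precision unused.

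**Conclusion.** The point holds in a modest form. The plan contains a data-driven rule for choosing covariates and leaves the rank of the two analyses open, so the deciding p-value and effect measure are not fixed before the arms are compared. The cost is discretion worth at most about 0.6 to 0.8 points of type I error over the chi-square in the same simulated trials (5.9 v 5.3, 5.7 v 4.9), and an unsecured gain of about 1 to 5 points of power. That gain matters most at the 7-point difference the plan itself considers, where chi-square power is about 71-72%. These sizes depend on an assumed cut-off, independent covariates and assumed prognostic strength. The finding does not threaten the validity of the trial or its sample size. It is an improvement available at no cost.

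**What to change.** Before any comparison of arms, amend Sections 10 and 13 as follows:
- Delete the imbalance trigger. Keep the table of standardised differences as description only.
- Name one primary analysis: a logistic model with arm and a fixed list of covariates already collected before allocation, for example sex, age, commune and the two baseline SEQ-12 scores. State how age is entered.
- Report a standardised risk difference from that model with its confidence interval, so that the effect stays on the scale of the power calculation.
- Keep the unadjusted chi-square as a supportive analysis.
- Make the inverse-probability-weighted analysis in the missing-data paragraph refer to this same main model.
- Include readiness to quit only if the baseline survey records it before randomisation; do not take it from later texts or quitline intake.

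If the team prefers to keep the chi-square as primary, it should say so and label a pre-specified adjusted model as supportive. That is the minimum needed to remove the discretion, though it gives up the precision.

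Cost: a few sentences in the plan. No extra participants, visits or data items.

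### The CACE leaves engagement undefined; if it means quitline/NRT use, a standard CACE credits the texts' direct effect to engagers, and the anticipated extra power is unsupported

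*Combined protocol and SAP*

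**What the plan says.** All of this is in Section 13 unless noted. The primary analysis is ITT. Its stated limitation is "As many in the encouragement arm will not participate, this ITT does not directly assess the intervention-attributable effect", so the plan adds a second analysis: "we will utilize a complier average causal effect (CACE) analysis to estimate intervention effects for those who engaged with the intervention". Four families of CACE method are listed and none is selected. No rule says who counts as engaged.

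On power, the same paragraph says "Below, we provide power for ITT analyses, and anticipate additional power when implementing the CACE". The only power figure is for the ITT: "We are powered to detect a 10% difference (alpha at 0.05) with 91% power".

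Two statements bear on what engagement means. The sample-size text says "all participants randomized to the intervention will receive the motivational messages. However, participants will choose whether or not to use the quitline and NRT", and it continues: "If we anticipate that 30% of the intervention will engage in quitline counseling and NRT, and that group will have a greater cessation rate" (20 to 25%). Section 17 describes the trial as an encouragement design meant to raise use of existing resources. Another sentence points to a different notion: "secondary analyses will explore dose-response effects among those with variable levels of adherence to the intervention".

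Section 5 (Innovation) expects the texting system to affect quitting directly. It reports that the earlier system worked whether or not smokers used NRT or a quitline.

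The ITT sentence itself reads "we will conduct an intent-to-treat analysis with all those randomized analyzed from MHV use at follow-up". MHV is not defined in the plan and is not one of its outcomes.

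**The concern.** A standard CACE, such as the instrumental-variable (Wald) estimator, divides the ITT difference by the difference in engagement between arms. It is valid only if assignment does nothing for people who do not engage (the exclusion restriction). If engagement is quitline/NRT use, the plan says the opposite, because everyone in the intervention arm gets texts that are expected to work by themselves. The gain among the roughly 70% who never use the quitline would then be reported as the effect in the 30% who do.

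At stake is the secondary estimate of benefit in engagers, which could be published as a large effect of quitline and NRT use that the plan's own inputs rule out. The power remark could also lead a reader to think the CACE rescues a marginal ITT result.

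**Working it through.** **Inputs from Section 13.** Control quit rate 10%; ITT difference 7 to 10 points; 30% of the intervention arm engage, and they quit at e = 20-25%; 600 analysed, so 300 per arm; two-sided alpha 0.05. **Assumptions not in the plan.** No control participant uses the quitline; the engagers' untreated quit rate u is varied.

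**1. The plan's power figure.** For 10% v 20% with 300 per arm, the pooled standard error is √(2 × 0.15 × 0.85/300) = 0.0292 and the unpooled one is √((0.09 + 0.16)/300) = 0.0289. With continuity correction, power = Φ((0.10 − 1/300 − 1.96 × 0.0292)/0.0289) = 91.5%; without it, 93.1%. The stated 91% is reproduced with the correction.

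**2. The power case already relies on a direct effect.** If only engagers gained and u = 10%, the ITT difference would be 0.30 × (10 to 15) = 3.0 to 4.5 points, with power of 21-39% (uncorrected formula). The direct effect needed in non-engagers is d = (ITT − 0.30(e − 0.10))/0.70. This runs from (0.07 − 0.045)/0.70 = 3.6 points (ITT 7, e = 25%) to (0.10 − 0.03)/0.70 = 10 points (ITT 10, e = 20%).

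**3. Bias of the standard CACE.** Wald = ITT/0.30 = (effect in engagers) + (0.70/0.30)d. Each point of d adds 2.33 points.

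| ITT (points) | Wald CACE (points) | Ratio to e − u, u = 10% | Ratio, u = 5% |
|---|---|---|---|
| 7 | 23.3 | 1.6 (e = 25%) to 2.3 (e = 20%) | 1.2 to 1.6 |
| 10 | 33.3 | 2.2 to 3.3 | 1.7 to 2.2 |

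The ratio rises when u exceeds 10%. With ITT 10, e = 22.5% and u = 15%, the effect in engagers is 7.5 points and the ratio is 33.3/7.5 = 4.4. This is feasible: non-engagers would quit at (0.20 − 0.30 × 0.225)/0.70 = 18.9%, against (0.10 − 0.30 × 0.15)/0.70 = 7.9% untreated.

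**4. Does the direction depend on u?** No overstatement requires u ≤ e − ITT/0.30. At ITT 10, 33.3 points exceeds any e in the plan's range, so this is impossible. At ITT 7 it needs e of at least 23.3% and u of at most e − 23.3%, which is 1.7% at e = 25%. Above ITT 7.5 no value of u works (0.075/0.30 = 25%).

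**5. Control uptake.** Section 5 says NRT is currently free to smokers, so some uptake is plausible. At an assumed 5%, the divisor is 0.25 and the Wald values become 28 and 40 points.

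**6. Other readings of engagement.** If it means receiving texts, uptake is about 100% and the CACE equals the ITT. If it means replying to texts, with reply rate r and non-repliers gaining a fraction f of what repliers gain, the ratio is 1 + f(1 − r)/r. For assumed r of 80% and 50% this is 1.0 at f = 0, 1.1 to 1.5 at f = 0.5, and 1.25 to 2.0 at f = 1.

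**7. Power of the CACE.** Simulated with 300 per arm and no control uptake (200,000 trials per scenario), ITT v Wald power was 93.6% v 93.6% and 93.5% v 93.1% with a direct effect and a 10-point ITT difference. It was 39.3% v 40.1% and 21.1% v 21.3% with no direct effect, and 93.6% v 94.5% when a 10-point ITT difference arose only in engagers. A likelihood CACE without covariates (1,500 trials) gave ITT v CACE power of 94.6% v 94.1% at 10 points and 72.7% v 72.5% at 7.

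**The case against.** The strongest reply is that the bias is conditional. The plan speaks of engaging with the intervention, and Sections 4 and 5 can be read as making the texting system the intervention. It commits to no estimator and never invokes the exclusion restriction. This stands: what the text shows is under-specification, and bias would follow only from a later choice. A reader might infer that the plan has already committed to a biased analysis, but it has not. The conditional point survives because the receipt reading does not fit an arm in which many are expected not to participate, and the plan uses engage for quitline and NRT use.

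A reader might also take 3.3-fold as the size of the error, or as its ceiling. The documents do not support that. It assumes a 10% untreated quit rate in engagers, which the plan does not give. People who choose to call a quitline could well have a higher rate, and step 3 then gives 4.4-fold.

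It might be inferred that control participants' quitline use goes unrecorded. Section 11 does not limit quitline tracking by arm, Section 9 lists quitline data as part of each subject's participation, and Aim 3 compares quitline access and NRT use between arms. Capture in both arms is already implied.

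On power, the plan only anticipates a gain, cites a source for it, and bases no decision on it. Gains from a covariate-assisted CACE are not excluded, so the remark is unsupported, not disproved. A power table may be missing from the text as read, but the plan's sentence promises only ITT power there.

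**Conclusion.** The point holds in conditional form. If engagement means quitline/NRT use and the estimator relies on the exclusion restriction, the plan's own expectation of a direct text effect makes the CACE too high. With no control uptake it would report 33 points at a 10-point ITT difference, which cannot be the effect in people who quit at 20-25%. At 7 points it would report 23, which escapes overstatement only if engagers quit at 23.3% or more and would almost never quit untreated (1.7% or less). The fold overstatement is about 1.6 to 3.3 at an untreated rate of 10%, smaller below that and larger above it. If engagement means replying to texts, bias arises only if non-repliers also gain.

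The anticipated extra power has no calculation behind it, and instrumental-variable or covariate-free likelihood estimation has essentially the ITT's power. The matter is confined to a secondary analysis. It gives no ground for doubting the primary ITT test or the sample size.

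**What to change.** 1. Delete the statement on additional power, or say that no gain over ITT is claimed.
2. Define engagement and the estimator, with its assumptions, before unblinding. If engagement is quitline/NRT use:
   - Measure it in both arms from the quitline data already planned, and note that these records may miss NRT obtained elsewhere.
   - Do not present the standard CACE as the effect in engagers. Label it an upper bound if the texts do no harm.
   - Accompany it with (ITT − (1 − D)d)/D and confidence intervals, where D is the between-arm difference in engagement and d the direct text effect. State that this assumes no defiers and a common d in those whose engagement assignment does not change. With D = 0.30 and d at 0, one third, two thirds and all of the ITT difference, it gives 33.3, 25.6, 17.8 and 10.0 points at ITT 10, and 23.3, 17.9, 12.4 and 7.0 at ITT 7.
   - Do not call d = ITT a lower bound, because engagers may gain less than non-engagers. In the 7.5-point example d is 18.9 − 7.9, about 11 points, and the truth lies below 10. Either carry d beyond the ITT difference or state the assumption as untestable.
3. As a minor correction, replace the MHV term in the ITT sentence with the cessation outcome.

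The cost is SAP wording, one sensitivity table, and linkage of quitline records to participants in both arms. The downside is that the secondary estimate becomes a range instead of a single figure.
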